7.6 Evaluation of an Adverse Event

All grade 3 and above adverse events will be entered into OnCore®, whether or not the event is believed to be associated with use of the study drug. Data about these events and their severity will be recorded using the NCI CTCAE v4.0.

The Investigator will assign attribution of the possible association of the event with use of the investigational drug, and this information will be entered into OnCore® using the classification system listed below:

Relationship	Attribution	Description
Unrelated to investigational drug/intervention	Unrelated	The AE is clearly NOT related to the intervention
	Unlikely	The AE is doubtfully related to the intervention
Related to investigational drug/intervention	Possible	The AE may be related to the intervention
	Probable	The AE is likely related to the intervention
	Definite	The AE is clearly related to the intervention

Signs or symptoms reported as adverse events will be graded and recorded by the Investigator according to the CTCAE. When specific adverse events are not listed in the CTCAE they will be graded by the Investigator as none, mild, moderate or severe according to the following grades and definitions:

- Grade 0 No AE (or within normal limits)
- Grade 1 Mild; asymptomatic or mild symptoms; clinical or diagnostic observations only; intervention not indicated
- Grade 2 Moderate; minimal, local, or noninvasive intervention (e.g., packing, cautery) indicated; limiting age-appropriate instrumental activities of daily living (ADL)
- Grade 3: Severe or medically significant but not immediately life-threatening; hospitalization or prolongation of hospitalization indicated; disabling; limiting self-care ADL
- Grade 4: Life-threatening consequences; urgent intervention indicated
- Grade 5: Death related to AE

7.6.1 NCI Common Terminology for Adverse Events (CTCAE)

An investigator who is a qualified physician will evaluate all adverse events according to the NCI Common Terminology for Adverse Events (CTCAE), version 4.0. Any adverse event which changes CTCAE grade over the course of a given episode will have each change of grade recorded on the adverse event case report forms/worksheets.

All adverse events regardless of CTCAE grade must also be evaluated for seriousness

Table 7.6 Evaluating Adverse Events

V4.0 CTCAE Grading	Grade 1	Mild; asymptomatic or mid symptoms; clinical or diagnostic observations only; intervention not indicated.
	Grade 2	Moderate; minimal, local or noninvasive intervention

		indicated; limiting age-appropriate instrumental ADL.
	Grade 3	Severe or medically significant but not immediately life-threatening; hospitalization or prolongation or hospitalization indicated; disabling; limiting self-care ADL.
	Grade 4	Life threatening consequences; urgent intervention indicated.
	Grade 5	Death related to AE
Seriousness	
A serious adverse event is any adverse event occurring at any dose or during any use of Merck product that:
 
†Results in death; or
 
†Is life threatening; or places the subject, in the view of the investigator, at immediate risk of death from the event as it occurred (Note: This does not include an adverse event that, had it occurred in a more severe form, might have caused death.); or
 
†Results in a persistent or significant disability/incapacity (substantial disruption of one’s ability to conduct normal life functions); or
 
†Results in or prolongs an existing inpatient hospitalization (hospitalization is defined as an inpatient admission, regardless of length of stay, even if the hospitalization is a precautionary measure for continued observation. (Note: Hospitalization [including hospitalization for an elective procedure] for a preexisting condition which has not worsened does not constitute a serious adverse event.); or
 
†Is a congenital anomaly/birth defect (in offspring of subject taking the product regardless of time to diagnosis);or
 
Is a new cancer; (that is not a condition of the study) or
 
Is an overdose (whether accidental or intentional). Any adverse event associated with an overdose is considered a serious adverse event. An overdose that is not associated with an adverse event is considered a non-serious event of clinical interest and must be reported within 24 hours to site UCSF CHR and Merck
 
Other important medical events that may not result in death, not be life threatening, or not require hospitalization may be considered a serious adverse event when, based upon appropriate medical judgment, the event may jeopardize the subject and may require medical or surgical intervention to prevent one of the outcomes listed previously (designated above by a †).
	
Duration	Record the start and stop dates of the adverse event. If less than 1 day, indicate the appropriate length of time and units	
Action taken	Did the adverse event cause the Merck product to be discontinued?	
Relationship to test drug	
Did the Merck product cause the adverse event? The determination of the likelihood that the Merck product caused the adverse event will be provided by an investigator who is a qualified physician. The investigator’s signed/dated initials on the source document or worksheet that supports the causality noted on the AE form, ensures that a medically qualified assessment of causality was done. This initialed document must be retained for the required regulatory time frame. The criteria below are intended as reference guidelines to assist the investigator in assessing the likelihood of a relationship between the test drug and the adverse event based upon the available information.
 
The following components are to be used to assess the
	

	relationship between the Merck product and the AE ; the greater the correlation with the components and their respective elements (in number and/or intensity), the more likely the Merck product caused the adverse event (AE):	
	Exposure	Is there evidence that the subject was actually exposed to the Merck product such as: reliable history, acceptable compliance assessment (pill count, diary, etc.), expected pharmacologic effect, or measurement of drug/metabolite in bodily specimen?
	Time Course	Did the AE follow in a reasonable temporal sequence from administration of the Merck product? Is the time of onset of the AE compatible with a drug-induced effect (applies to trials with investigational medicinal product)?
	Likely Cause	Is the AE not reasonably explained by another etiology such as underlying disease, other drug(s)/vaccine(s), or other host or environmental factors

7.7 Follow-up of Adverse Events

All adverse events will be followed with appropriate medical management until resolved. Patients removed from study for unacceptable adverse events will be followed until resolution or stabilization of the adverse event. For selected adverse events for which administration of the investigational drug was stopped, a re-challenge of the subject with the investigational drug may be conducted if considered both safe and ethical by the Investigator.

7.8 Adverse Events Reporting

All adverse events, whether or not unexpected, and whether or not considered to be associated with the use of the study drug, will be entered into OnCore®, as noted above.

The Investigator will assess all adverse events and determine reportability requirements to the UCSF Data and Safety Monitoring Committee (DSMC) and UCSF’s Institutional Review Board, the Committee on Human Research (CHR); and, when the study is conducted under an Investigational New Drug Application (IND), to the Food and Drug Administration (FDA) if it meets the FDA reporting criteria.

All adverse events entered into OnCore® will be reviewed by the Helen Diller Family Comprehensive Cancer Center Site Committee on a weekly basis. The Site Committee will review and discuss at each weekly meeting the selected toxicity, the toxicity grade, and the attribution of relationship of the adverse event to the administration of the study drug(s).

All grade(s) 3-5 adverse events entered into OnCore® will be reviewed on a monthly basis at the Site Committee meetings. The Site Committee will review and discuss the selected toxicity, the toxicity grade, and the attribution of relationship of the adverse event to the administration of the study drug(s).

In addition, all suspected adverse reactions considered “serious” entered into OnCore®, will be reviewed and monitored by the Data and Safety Monitoring Committee on an ongoing basis and discussed at DSMC meetings, which take place every six weeks.

For a detailed description of the Data and Safety Monitoring Plan for a Multicenter Phase 2 or 3 Institutional Study at the Helen Diller Comprehensive Cancer Center please refer Appendix 4 Multicenter Institutional Studies.\

7.8.1 Definition of an Overdose for This Protocol and Reporting of Overdose to the study PI and Merck.

For purposes of this trial, an overdose will be defined as any dose exceeding the prescribed dose for pembrolizumab by 20% over the prescribed dose. No specific information is available on the treatment of overdose of pembrolizumab. In the event of overdose, the subject should be observed closely for signs of toxicity. Appropriate supportive treatment should be provided if clinically indicated.

If an adverse event(s) is associated with (“results from”) the overdose of a Merck product, the adverse event(s) is reported as a serious adverse event, even if no other seriousness criteria are met.

If a dose of Merck’s product meeting the protocol definition of overdose is taken without any associated clinical symptoms or abnormal laboratory results, the overdose is reported as a non-serious Event of Clinical Interest (ECI), using the terminology “accidental or intentional overdose without adverse effect.”

All reports of overdose with and without an adverse event must be reported within 2 working days hours to Merck Global Safety. ([REDACTED])

7.8.2 Serious Adverse Events

A serious adverse event is any adverse event occurring at any dose or during any use of Merck’s product that:

- Results in death;
- Is life threatening;
- Results in persistent or significant disability/incapacity;
- Results in or prolongs an existing inpatient hospitalization;
- Is a congenital anomaly/birth defect;
- Is a new cancer (that is not a condition of the study);
- Is associated with an overdose;
- Is another important medical event

Refer to Table X for additional details regarding each of the above criteria.

Progression of the cancer under study is not considered an adverse event unless it results in hospitalization or death.

Any serious adverse event, or follow up to a serious adverse event, including death due to any cause other than progression of the cancer under study that occurs to any subject from the time the consent is signed through 30 days following cessation of treatment, or the initiation of new anti-cancer therapy, whichever is earlier, whether or not related to Merck product, must be reported within 24 hours to the Sponsor and within 2 working days to Merck Global Safety.

Non-serious Events of Clinical Interest will be forwarded to Merck Global Safety and will be handled in the same manner as SAEs.

Additionally, any serious adverse event, considered by an investigator who is a qualified physician to be related to Merck product that is brought to the attention of the investigator at any time outside of the time period specified in the previous paragraph also must be reported immediately to the Sponsor and to Merck.

SAE reports and any other relevant safety information are to be forwarded to the Merck Global Safety [REDACTED]

A copy of all 15 Day Reports and Annual Progress Reports is submitted as required by FDA, European Union (EU), Pharmaceutical and Medical Devices agency (PMDA) or other local regulators. Investigators will cross reference this submission according to local regulations to the Merck Investigational Compound Number (IND, CSA, etc.) at the time of submission. Additionally investigators will submit a copy of these reports to Merck & Co., Inc. [REDACTED] [REDACTED] at the time of submission to FDA.

All subjects with serious adverse events must be followed up for outcome.

7.8.3 Reporting of Pregnancy and Lactation to the Sponsor and to Merck

Although pregnancy and lactation are not considered adverse events, it is the responsibility of investigators or their designees to report any pregnancy or lactation in a subject (spontaneously reported to them), including the pregnancy of a male subject's female partner that occurs during the trial or within 120 days of completing the trial, or 30 days following cessation of treatment if the subject initiates new anticancer therapy, whichever is earlier. All subjects and female partners of male subjects who become pregnant must be followed to the completion/termination of the pregnancy. Pregnancy outcomes of spontaneous abortion, missed abortion, benign hydatidiform mole, blighted ovum, fetal death, intrauterine death, miscarriage and stillbirth must be reported as serious events (Important Medical Events). If the pregnancy continues to term, the outcome (health of infant) must also be reported.

Such events must be reported within 2 working days to Merck Global Safety. [REDACTED]

7.9 Expedited Reporting

Reporting to the Data and Safety Monitoring Committee

If a death occurs during the treatment phase of the study or within 30 days after the last administration of the study drug(s) and it is determined to be related either to the study drug(s) or to a study procedure, the Investigator or his/her designee must notify the DSMC Chair (or qualified alternate) within 1 business day of knowledge of the event. The contact may be by phone or e-mail.

Reporting to UCSF Committee on Human Research (Institutional Review Board)

The Principal Investigator must report events meeting the UCSF CHR definition of "Unanticipated Problem" (UP) within 10 business days of his/her awareness of the event.

Reporting to Sponsor – Merck & Co

Any serious adverse event, that are unexpected and related, or follow up to a serious adverse event, including death due to any cause other than progression of the cancer under study that occurs to any subject from the time the consent is signed through 30 days following cessation of treatment if the subject initiates new anticancer therapy, whichever is earlier, whether or not related to the Sponsor's product, must be reported within 24 hours to the Sponsor either by electronic media or paper. Sponsor Contact information can be found in the Investigator Trial File Binder (or equivalent).

Additionally, any serious adverse event, considered by an investigator who is a qualified physician to be related to the Sponsor's product that is brought to the attention of the investigator at any time outside of the time period specified in the previous paragraph also must be reported immediately to the Sponsor.

Expedited Reporting to the Food and Drug Administration

If the study is being conducted under an IND, the Sponsor-Investigator is responsible for determining whether or not the suspected adverse reaction meets the criteria for expedited reporting in accordance with Federal Regulations (21 CFR §312.32).

The Investigator must report in an IND safety report any suspected adverse reaction that is both serious and unexpected. The Sponsor-Investigator needs to ensure that the event meets all three definitions:

- Suspected adverse reaction
- Unexpected
- Serious

If the adverse event does not meet all three of the definitions, it should not be submitted as an expedited IND safety report.

The timeline for submitting an IND safety report to FDA is no later than 15 calendar days after the Investigator determines that the suspected adverse reaction qualifies for reporting (21 CFR 312.32(c)(1)).

Any unexpected fatal or life-threatening suspected adverse reaction will be reported to FDA no later than 7 calendar days after the Investigator's initial receipt of the information (21 CFR 312.32(c)(2)).

Any relevant additional information that pertains to a previously submitted IND safety report will be submitted to FDA as a Follow-up IND Safety Report without delay, as soon as the information is available (21 CFR 312.32(d)(2)).

8.0 Statistical Considerations and Evaluation of Results

This trial will determine whether epigenetic priming may enhance the effects of PD-1 inhibitors in patients with ER+ metastatic breast cancer who have progressed on prior hormone therapy and chemotherapy. The trial will contain three arms. Within each arm we will determine whether epigenetic priming will required prolonged pre-exposure to epigenetic modulators or concomitant administration.

Three arms will be tested, with each independent assessment. Patients will be stratified by prior number of hormonal therapy and chemotherapy, then randomized across arms by [name], UCSF.

8.1 Response rates to chemotherapy in breast cancer are less than 20%. Historical response rates to pembrolizumab and MPDL3280A have been 18% and 19%, respectively, in patients whose tumors are PD-L1 positive. Hence, we expect the response rate for unselected patients and patients with no PD-L1 expression would be 10% or less. In contrast, we anticipate that vorinostat will increase the response rate to 30%**Sample Size and Power Estimate**

Response rates to hormonal therapy and MTOR or HDAC inhibitors have been reported as 5-20% (19% for VOR-Tam, 6% for entinostat-exemestane, 12% for exemestane-everolimus). Given the recent additions to hormonal therapy this trial will treat a patient population that has received more lines of therapy than these trials, however we are interested in an ORR of >30%.

8.2 For each arm: Using an Optimal Simon's two-stage design (Simon, 1989), the null hypothesis (H₀) that the true response rate is 10% will be tested against a one-sided alternative. In the first stage, 10 patients will be accrued and a decision will be made to continue or stop accrual based on the observed objective response rate (ORR). If there are 0 or 1 objective responses at 24 weeks in these 10 patients, accrual to this arm of the study will be stopped. Otherwise, 19 additional patients will be accrued for a total of n=29. We estimate that each regimen under evaluation will achieve ORR ≥ 30%. This study is designed to have an alpha of 0.0471, and a power of 80.5% to test the null hypothesis H₀: ORR = 10% against an alternative hypothesis, H_A: ORR = 30%, where ORR is defined as CR, PR, or SD ≥ 24 weeks where arms are enrolled independently.**Interim Analyses**

In addition to the interim analysis for efficacy that is built into the Simon 2-stage design (see above), in each arm we will evaluate the need for dose modification after 6 patients have been enrolled. If 2 or more patients have a grade 3 non-hematologic toxicity that is clearly related to pembrolizumab, this agent will be reduced to 75%. Dose modification of vorinostat should be undertaken as per dose modification guidelines, a prior study with vorinostat and tamoxifen suggest that there is a high interpatient variability and tolerance and vorinostat will be adjusted per dose modification guidelines individually.

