In a Phase II clinical trial, we evaluated the role of vorinostat (VOR) in reversing hormone therapy resistance in advanced breast cancer². In a single arm study, 43 patients (median age 56 years (31–71)) were treated. A total of 25 patients (58%) received prior adjuvant tamoxifen (TAM), 29 (67%) progressed on at least one prior chemotherapy regimen, 42 (98%) progressed after one, and 23 (54%) after two aromatase inhibitors. The objective response rate by RECIST criteria was 19% and the clinical benefit rate (response or stable disease \geq 24 weeks) was 40%. The median response duration was 10.3 months (confidence interval: 8.1–12.4). Histone hyperacetylation and higher baseline HDAC2 levels correlated with response and responses were mainly seen in the 56% of patients who had a meaningful change in acetylation with vorinostat. Preclinical studies have further suggested that hormonal therapy must be continued even in the presence of an HDAC inhibitor.

1.3.1.2 Prior studies with other HDAC inhibitors in breast cancer:

[figure not shown]
A second phase II (ENCORE 301) trial evaluated entinostat and exemestane, and treated patients with advanced estrogen receptor (ER)-positive breast cancer⁶⁶. This study recently received Breakthrough Therapy designation from the FDA for its potential to reverse resistance to hormonal therapies. The median PFS was 4.3 months versus 2.3 months, for entinostat and placebo, respectively (HR = 0.73; P = 0.06). The median overall survival in the combination arm was 28.1 m compared to 19.8 m in the exemestane arm (HR = 0.59; P = 0.036). The objective response rate to the combination was 6.3%, while to exemestane alone was 4.6% (P = 0.58). While these two studies cannot be compared directly, the preclinical studies and the clinical studies, as well as the current landscape of standard of care, will make the combination with tamoxifen more likely effective. The combination with tamoxifen will also allow enrollment of premenopausal women.

Hence the combination of HDAC inhibitors and PD-1 inhibitors may further result in an enhancement of anti-tumor efficacy of PD-1 inhibitors^{6,67}. Based on the established role of HDAC inhibitors in reversing hormone therapy resistance to antiestrogens and aromatase

inhibitors and the provocative role of HDAC inhibitors in modulating tumor immunity, we propose to test the role of epigenetic immune priming (EIP) in acquired hormone therapy resistance.

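### The 10% null is argued from response rates, but the endpoint counts stable disease; on nearly that endpoint the protocol itself reports 40% for vorinostat plus tamoxifen

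*Combined protocol and SAP*

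**What the plan says.** The primary endpoint counts stable disease wherever it is defined: in the synopsis objective, in Sections 2.1 and 2.4.1, in Section 8.2 ("where ORR is defined as CR, PR, or SD ≥ 24 weeks where arms are enrolled independently") and in Section 8.3.2, which counts patients who are SD or better at 24 weeks among all those randomized to the arm.

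The two rates are argued in the text around Section 8.1:

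- **PD-1/PD-L1 agents:** "Historical response rates to pembrolizumab and MPDL3280A have been 18% and 19%, respectively, in patients whose tumors are PD-L1 positive". The null follows from this: "Hence, we expect the response rate for unselected patients and patients with no PD-L1 expression would be 10% or less".
- **Alternative:** "In contrast, we anticipate that vorinostat will increase the response rate to 30" per cent.
- **Hormonal combinations:** "Response rates to hormonal therapy and MTOR or HDAC inhibitors have been reported as 5-20% (19% for VOR-Tam, 6% for entinostat-exemestane", and 12% for exemestane-everolimus.
- **Population:** "this trial will treat a patient population that has received more lines of therapy than these trials".

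Section 8.2 then sets, for each arm, a Simon two-stage design with 10 patients, stopping at 0 or 1 responses, and otherwise 29 in total. It states alpha 0.0471 and power 80.5%. It does not print the final cutoff. Section 8.3.2 rejects the null when the lower limit of an Agresti-Coull 95% CI exceeds 10%, and then calls the regimen good enough to study further.

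The prior vorinostat trial is described in Section 1.3.1.1: "In a single arm study, 43 patients" were treated, with a RECIST objective response rate of 19% and a clinical benefit rate (response or SD of at least 24 weeks) of 40%. Section 8 uses the 19% and does not mention the 40%.

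**The concern.** A null rate should be one that would be uninteresting on the outcome actually counted. Here the outcome is disease control to 24 weeks, while the argument for 10% and 30% concerns response. Two of the supporting figures certainly exclude SD: the 19% for vorinostat-tamoxifen (Section 1.3.1.1) and the 6% for entinostat-exemestane (Section 1.3.1.2). For the 18% and 19% from which the 10% is derived, and for the 12%, exclusion of SD is inferred from the term used.

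Arms A and B both contain vorinostat and tamoxifen. On nearly the tested endpoint, the only figure in the protocol for that pair lies above both the null and the alternative. The threshold governs whether an arm passes stage 1 and whether it is recommended for further study. It also bears on the stated aim: "This trial will determine whether epigenetic priming may enhance the effects of PD-1 inhibitors". If the backbone alone may exceed 10%, rejecting 10% says little about what pembrolizumab or priming contributes.

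**Working it through.** **1. Reproduce the stated design.** Inputs from Section 8.2: n1=10, continue if 2 or more, n=29. For a true rate p and final cutoff c,

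P(positive) = Σ (x=2 to 10) C(10,x) p^x (1−p)^(10−x) × P[Bin(19,p) ≥ c−x].

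At p=0.10 and c=6, the terms are:

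- x=2: 0.1937 × 0.1150 = 0.0223
- x=3: 0.0574 × 0.2946 = 0.0169
- x=4: 0.0112 × 0.5797 = 0.0065
- x=5: 0.0015 × 0.8649 = 0.0013
- x≥6: 0.0001

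The sum is 0.0471. At p=0.30 the same formula gives 0.805. Both stated figures reproduce, so the implied cutoff is at least 6/29. Cutoffs of 5 and 7 give alpha 0.1016 and 0.0177.

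**2. Check the rule in Section 8.3.2.** With z=1.96, ñ = 29 + z² = 32.84 and p̃ = (x + z²/2)/ñ. The lower limit is p̃ − z√(p̃(1−p̃)/ñ).

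- x=6: 0.2412 − 0.1463 = 0.095, below 10%
- x=7: 0.2716 − 0.1521 = 0.120, above 10%

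The CI rule therefore needs at least 7/29. In the two-stage design that gives alpha 0.0177 and power 73.9%, not the stated pair.

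**3. The benchmark and its uncertainty.** With a denominator of 43, only 17/43 (39.5%) rounds to 40% and only 8/43 (18.6%) rounds to 19%. The exact (Clopper-Pearson) 95% CIs are 25.0 to 55.6% and 8.4 to 33.4%. The counts are inferred from the rounded percentages.

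**4. What the design does if pembrolizumab adds nothing,** so that an ER-positive arm has the backbone's rate:

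| True rate | Pass stage 1 | Positive, ≥6/29 | Positive, ≥7/29 | Basis of rate |
|---|---|---|---|---|
| 40% | 95% | 95% | 94% | reported clinical benefit rate |
| 25% | 76% | 65% | 54% | lower 95% limit of that rate |
| 20% | 62% | 43% | 31% | assumption |
| 15% | 46% | 20% | 11% | assumption |

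At 40% the chance of stopping at stage 1 is 0.6^10 + 10 × 0.4 × 0.6^9 = 0.0060 + 0.0403 = 0.046. The stage-1 column assumes that SD counts at that look, which the stage-1 sentence does not say outright.

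**5. Would testing CR+PR at 10% settle it?** At the backbone's 19% the design is positive with probability 38% (≥6/29) or 26% (≥7/29). A justified null would still be needed.

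**6. Illustrative higher nulls at 10 then 29 patients,** with a 20-point gain kept. These nulls and alternatives are assumptions:

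| Null vs alternative | Stop at stage 1 | Positive | Alpha | Power |
|---|---|---|---|---|
| 20% vs 40% | ≤1/10 | ≥10/29 | 0.047 | 77% |
| 25% vs 45% | ≤2/10 | ≥12/29 | 0.036 | 69% |
| 30% vs 50% | ≤2/10 | ≥14/29 | 0.029 | 64% |
| 40% vs 60% | ≤3/10 | ≥17/29 | 0.032 | 63% |

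**The case against.** **Comparability.** The 40% comes from one single-arm study of 43 patients, whose vorinostat dose and schedule the protocol does not give. Section 8 expects patients with more prior therapy. Section 8.3.2 is also somewhat stricter, because a responder who progresses before week 24 counts in the 40% but not there. All of this stands, and the backbone's rate here may well be lower. It does not supply an SD-inclusive rate near 10%, and Section 8 offers none.

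**Source of the null.** The 10% is drawn from the PD-1/PD-L1 rates, and the documents do not define those beyond calling them response rates. That they exclude SD is the natural reading but is not proved. Those rates also describe PD-1/PD-L1 agents without the vorinostat-tamoxifen backbone, so even a deliberate PD-1 screening null leaves the backbone's own disease control unaccounted for.

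**No superiority claim.** A reader might infer that the protocol claims an advantage over vorinostat plus tamoxifen. It does not; Section 8.3.2 concludes only that further study is warranted. The difficulty lies in the broader aim stated at the head of Section 8.

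**Other stronger readings.** A reader might conclude that the sample-size arithmetic is wrong or that the type I error is 95%. Neither follows. Alpha is 0.0471 at the stated null with a cutoff of 6/29, and the 95% is conditional on a true 40% with no pembrolizumab effect. Nor can the 40% be carried to Arm C, which is ER-negative and has no tamoxifen.

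**Conclusion.** The point holds for Arms A and B. The threshold rests on rates described as response rates and is applied to an outcome that also counts stable disease, and 10% is not shown to be uninteresting on that outcome. It lies below the 25% lower limit of the protocol's own nearest benchmark. If pembrolizumab added nothing, the chance of a positive arm would be 54 to 95% across backbone rates of 25 to 40%, depending on the rate and on which cutoff is applied. Below 25% the figures rest on assumed rates and fall to 11% at 15% with the CI rule. The true backbone rate in this population is unknown.

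A separate fault is certain: the CI rule in Section 8.3.2 does not deliver the alpha and power stated in Section 8.2.

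For Arm C the same mismatch exists, but the documents give no SD-inclusive benchmark, so its size cannot be stated.

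**What to change.** 1. **Sections 8.1 and 8.2, Arms A/B.** Keep the stated primary endpoint. Replace the 10% null with one justified in writing from SD-inclusive data: the 40% and its CI, with an explicit allowance for heavier pretreatment. Restate the stage-1 rule, final cutoff, alpha and power at n=29.
2. **Sections 8.2 and 8.3.2.** State that the Simon final cutoff is the decision rule (at least 6/29 for the present 10% vs 30% design, or its replacement) and that the Agresti-Coull interval is descriptive.
3. **Section 8.3.2, Arms A/B.** Limit the conclusion to activity above the null rate. Say that rejection does not show that pembrolizumab adds to vorinostat plus tamoxifen, or that priming enhances PD-1 inhibition. Report CR+PR and CR+PR+SD of at least 24 weeks beside the 19% and 40%, with their CIs.
4. **Stage 1.** State that the count at 10 patients uses the same definition as the final test.
5. **Arm C.** Justify its null separately on the endpoint tested.

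Cost: no extra patients or procedures, but an amendment with the approvals that Section 9.4 requires. Stated power becomes less favourable, at 63 to 77% in the illustrations above instead of 80.5%. Restoring 80% would need more patients and is not proposed here. Testing CR+PR instead is open to the sponsor, but it changes the primary endpoint and still needs a justified null, because 10% is below the backbone's 19%.
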